8.2 Study Populations for Analysis

- Evaluable set: Subjects who received all 4 doses and in whom all blood samples were collected.
- Per Protocol set (PP): A subset of evaluable subjects who have completed all 4 doses of treatment and evaluations through Visit 5 and who follow the protocol without any major deviation(s). A subject who received Decadron will be excluded.

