5.4 SUBJECT WITHDRAWAL OR TERMINATION

A subject may be withdrawn from the study for the following medical or administrative reasons:

- Occurrence of an adverse event (AE) that represents an unacceptable risk to the subject and when continued participation in the investigational study is not warranted, in the judgment of the investigator or Sponsor Medical Monitor. The investigator must follow the subject until the AE resolves or is stable, unless the subject is lost to follow up.
- Treatment with a prohibited concomitant medication other than the use of appropriate medications for the treatment of AEs under direction of the investigator.
- Subject noncompliance, defined as refusal or inability to adhere to the trial schedule or procedures.
- At the request of the subject (e.g., subject withdraws consent), investigator, Sponsor, or regulatory authority.
- Pregnancy.

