5.4.2 HANDLING OF PARTICIPANT WITHDRAWALS OR TERMINATION

Subjects will be encouraged to complete the study and all assessments. Subjects may voluntarily withdraw at any time, and the investigator may discontinue individual subjects from the study at any time.

Approximately 45 subjects (1:1 ratio of GRF6021 to placebo) will be enrolled in the study with the aim of having 40 evaluable subjects. Evaluable subjects are those who received all 4 doses and had all blood draws for assessment of the primary endpoint. Subjects who discontinue or are unblinded may be replaced. Subjects who withdraw or are withdrawn during screening will be replaced.

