7.3.4 BASELINE: ON-SITE/TREATMENT

The on-site Baseline assessments will be gathered prior to the first infusion on Day 1. After the first infusion on Day 1, the subject will be discharged from the facility and come back the following morning (Day 2) for the inpatient period. The inpatient treatment period is 2 days during which each subject will receive 3 additional doses of 250 mL of their assigned treatment allocation (i.e., either GRF6021 or placebo).

Visits 3 through 5, Treatment (Days 1-3):

- Perform the following procedures on each day *prior* to administering (the first) study infusion:
 - Review AEs and concomitant medications.
 - 12-lead ECG (**Day 1 and 3 Only**).
 - Collect sample for CyTOF assessment (**Including second infusion on Day 2**).

- Obtain samples for proteomic assessments; fasting samples preferred (**Including second infusion on Day 2**).
- Collect vital signs (BP, HR, RR, and body temperature) (**Including second infusion on Day 2**).
- Targeted physical exam (**Day 1 and 3 Only**).
- Pregnancy testing for WOCBP (**Day 1 Only**).
- Administer 3D-CAM, SRS, and WOMAC (**Day 1 and 3 Only**).
- ActiGraph device data collection (**Day 1 and 3 Only**).
- Administer study treatment per the GRF6021 Infusion Administration Manual:
 - On the day before surgery (**Day 1**).
 - On the day of surgery within 4 hours before surgery start (first incision) (**Day 2**).
 - On the day of surgery upon arrival in the PACU (within 5 hours after the first incision) (**Day 2**).
 - On the day after surgery (**Day 3**).
- Perform the following assessments following each infusion start:
 - BP and HR at 15, 30, 45, and 60 min after infusion start.
 - Body temperature and RR at 60 minutes.
 - Collection of perioperative data (**Day 2 Only**, after second infusion).
 - Opioid consumption assessment (**Days 2 and 3 Only**).
 - 12-lead ECG (**Day 3+1 Only**, after end of last infusion).
 - Exit lab panel including pregnancy test (**Day 3 Only**, after end of last infusion).
 - Administer 3D-CAM (**Day 2 Only**, after second infusion).

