7.3 Sample Size Justification

As detailed in the protocol, the goal is to enroll a total of approximately 45 subjects with the aim of having 40 evaluable subjects randomized in a 1:1 ratio to active treatment or placebo groups. Due to the coronavirus disease 2019 (COVID-19) pandemic, enrollment ended with 37 evaluable subjects. Evaluable subjects are those who received all 4 doses and had all blood draws for assessment of the primary endpoint. Previous work demonstrated that a sample size of approximately 40 subjects enabled the detection of clinically-relevant immunomodulatory changes, such as changes in signaling downstream of immune receptors, including interleukin-1 and toll-like receptor 4 ([Aghaeepour 2017](#), [Davis 2020](#)).

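### SAP 8.2 excludes subjects for missing dose 4, although every CyTOF and proteomic sample precedes it, and excludes them from CyTOF Dataset 2 for missing later doses or draws that cannot affect it

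*SAP*

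**What the plan says.** SAP 8.2 gives two analysis sets for the CyTOF, proteomic and ActiGraph endpoints. The first is "Evaluable set: Subjects who received all 4 doses and in whom all blood samples were collected". The second, Per Protocol, is "A subset of evaluable subjects who have completed all 4 doses of treatment and evaluations through Visit 5", with further exclusions for major deviations and for one named medication. Neither is designated as the main set. The all-randomized set in protocol 10.3 has no counterpart in this SAP, and protocol 10.4.1 directs endpoint summaries to the Evaluable and/or Per Protocol sets.

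The Evaluable definition varies between sections. Protocol 5.4.2 reads "Evaluable subjects are those who received all 4 doses and had all blood draws for assessment of the primary endpoint", and protocol 10.1 and SAP 7.3 agree with it. Protocol 10.3 requires the four doses only. SAP 8.2 requires the doses and all blood samples, without saying which samples.

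On timing, protocol 7.3.4 lists "Collect sample for CyTOF assessment" among the procedures done before infusion on each treatment day, with the addition "Including second infusion on Day 2". Proteomic samples are handled in the same way. SAP 7.1 places both kinds of sample at Visits 3, 4a, 4b and 5 only. SAP 8.4.1 builds Dataset 1 from changes to Visits 4b and 5, and Dataset 2 from the change between Visit 3 and Visit 4a.

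**The concern.** A subject can have every CyTOF and proteomic sample, miss dose 4, and be left out of both sets. A subject with good Visit 3 and Visit 4a samples can be left out of Dataset 2 because of something that happened after Visit 4a. In both cases the outcome had been observed before the event that causes the exclusion.

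The reason for missing a dose or draw may be related to treatment. Protocol 5.4 lists as a ground for withdrawal "Occurrence of an adverse event (AE) that represents an unacceptable risk to the subject", and protocol 5.4.2 adds "Subjects who discontinue or are unblinded may be replaced". If such losses differ between arms, the analyzed groups are no longer the randomized groups. Even if they do not differ, usable samples are lost from a small pilot. The flow diagram in SAP 8.1 and the comparison of discontinuation reasons in protocol 10.4.4 would show the losses but would not restore the subjects.

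ActiGraph is outside this point, because its recording continues after dose 4.

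**Working it through.** **Order of samples and doses** (protocol 7.3.4 and 15.1; SAP 7.1). Visit 3 sample, dose 1, Visit 4a sample, dose 2, surgery, Visit 4b sample, dose 3, Visit 5 sample, dose 4.

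| Sample | Doses already given | Used in Dataset 2 |
|---|---|---|
| Visit 3 | 0 | yes |
| Visit 4a | 1 | yes |
| Visit 4b | 2 | no |
| Visit 5 | 3 | no |

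Note X1 in protocol 15.1, read literally, puts all Day 2 pre-infusion procedures before the first Day 2 infusion, which would make the Visit 4b count 1. On either reading every sample precedes dose 4. Dose 4 can affect no CyTOF or proteomic value. Only dose 1 can affect Dataset 2. Doses 1 to 3 can affect Dataset 1.

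**Subjects at stake.** The plan gives about 45 to be enrolled, 40 evaluable as the aim, and 37 evaluable achieved (SAP 7.3). It does not give the number randomized. If k excluded subjects have usable samples, the share of usable subjects lost is k/(37 + k):

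- k = 0: 0/37 = 0%
- k = 1: 1/38 = 2.6%
- k = 2: 2/39 = 5.1%
- k = 5: 5/42 = 11.9%
- k = 8: 8/45 = 17.8%

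The upper end assumes that all 45 planned subjects were randomized and that all eight excluded subjects have usable samples.

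**Possible bias (illustration only).** The shift in one arm's mean is the fraction dropped times the difference between dropped and retained subjects. Assume 22 subjects in the arm.

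- 1 dropped, difference 0.5 SD: (1/22) × 0.5 = 0.02 SD
- 3 dropped, difference 1 SD: (3/22) × 1 = 0.14 SD

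For scale, a two-sided t-test on a single feature at alpha 0.05 with 80% power and 18 v 19 subjects detects 0.95 SD.

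**Which samples Dataset 1 needs.** SAP Table 2 lists 21 cell types and 11 markers. Two postoperative visits give 21 × 2 = 42 frequency features and 21 × 11 × 2 = 462 signaling features, 504 in all. The frequency features are referenced to Visit 3. For the signaling features SAP 8.4.1 gives two references: the Dataset 1 bullet uses Visit 3, and a later paragraph uses Visit 4a. Features lacking when one sample is missing:

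| Missing sample | Signaling reference Visit 4a | Signaling reference Visit 3 |
|---|---|---|
| Visit 3 | 42 (8.3%) | 504 (100%) |
| Visit 4a | 462 (91.7%) | 0 |
| Visit 4b or Visit 5 (either one) | 252 (50%) | 252 (50%) |

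Requiring Visits 4b and 5 for Dataset 1 therefore has a measurement reason on both readings. Whether Visit 4a is needed depends on which reading is meant.

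**The case against.** The four-dose rule is deliberate. It appears in protocol 5.4.2, 10.1 and 10.3 and in SAP 7.3, and studying the full regimen in completers is a defensible aim for a mechanistic pilot that is not designed for significance. One cohort for both CyTOF datasets, proteomics and a combined model also makes the results comparable. The number excluded may be zero, and the treatment-related route is inferred from a general list of withdrawal reasons. The protocol manages tolerability by adjusting infusion rate and time and cites a very low frequency of infusion reactions.

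Most of this limits the size of the problem. None of it gives a reason to condition a value on a dose given after the value was measured. The loss of a common cohort is a real cost of the change.

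A reader might go further and infer that the whole dose requirement should be dropped for Dataset 1. The timing argument does not support that. Doses 1 to 3 precede the Visit 5 sample and are the exposure under study, so admitting subjects who missed one of them changes the estimand.

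A reader might also infer that the rule caused the shortfall from 40 to 37. The SAP gives another cause: "Due to the coronavirus disease 2019 (COVID-19) pandemic, enrollment ended with 37 evaluable subjects".

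Finally, SAP 8.2 taken literally would require the exit lab panel, which is drawn after dose 4. SAP 7.3 and protocol 5.4.2 limit the draws to those for the primary endpoint, so this is loose wording to correct and not evidence that the panel is meant to decide evaluability.

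**Conclusion.** The point holds for dose 4 in all CyTOF and proteomic analyses, and for doses 2 to 4 and the Visit 4b and 5 draws in Dataset 2. There the sets in SAP 8.2 select on events after the outcome was measured. This rests on the visit order in the documents and is the same under either reading of the Visit 4b timing.

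The practical effect is uncertain. The documents do not show that any subject was lost in this way or that losses differed by arm. The percentages and the bias range above rest on assumed inputs, and any bias is probably small beside what the study can detect. The change is still worth making, because the rule has no measurement rationale and costs little to correct.

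**What to change.** First settle two matters of definition. State whether Dataset 1 endogenous signaling changes are referenced to Visit 3 or to Visit 4a, since this decides whether a Visit 4a sample is needed. Reconcile the Evaluable definitions in protocol 10.3, protocol 5.4.2 and 10.1, SAP 7.3 and SAP 8.2.

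Then amend SAP 8.2:

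1. Dataset 2: the main set is all randomized subjects who started infusion 1 and have Visit 3 and Visit 4a samples, analyzed as randomized.
2. Dataset 1, proteomic and combined models: do not exclude a subject only because dose 4 was missed or incomplete. Require only the CyTOF or proteomic samples that the model uses, not the exit lab panel. Whether to admit subjects who missed dose 1, 2 or 3 is an estimand choice for the sponsor and could be a sensitivity analysis.
3. Keep Evaluable and Per Protocol as named sensitivity analyses, and show exclusions by arm and reason in the planned flow diagram. Record the departure from protocol 10.4.1 in the SAP and the clinical study report. If data are already unblinded, label the change post hoc.

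The cost is SAP wording and, if any excluded subject has stored samples, their assay. Dataset 2 may have a slightly different population from the other models, and a few partially dosed subjects would enter the main estimate. The Evaluable sensitivity analysis shows their influence.

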8.3 Methods for Handling Missing Data

In order to minimize missing data, every effort will be made to obtain required data for all randomized subjects at each scheduled evaluation. However, in the event that more than 5% of data are missing, imputation methods will be used for the analysis of the primary endpoint only.

8.4 Efficacy Analyses

8.4.1 Primary Endpoint

Determination of functional responses in precisely phenotyped cell subsets may be obtained utilizing CyTOF, a highly parameterized single-cell based method. Thus, CyTOF can comprehensively characterize phenotypic and functional alterations of the human immune system as they occur *in vivo*.

Serial blood samples collected at baseline and all 3 perioperative time points (Visits 3, 4a, 4b, and 5) will be processed using a standardized protocol for fixation (Smart Tube, San Carlos, CA), storage, and antibody (Ab) staining of whole-blood samples for CyTOF (Gaudillière 2014, Fragiadakis 2015, Gaudillière 2015). At each point, samples will be either left unstimulated (for quantification of cell frequency and endogenous intracellular activities) or stimulated with a series of extracellular ligands (for analysis of evoked intracellular signaling responses). Cell frequency and signaling activities will be quantified in all major innate and adaptive immune cell subsets (Table 2 [left]). In addition, the intracellular expression of specific signaling markers will be simultaneously quantified per single cell (Table 2 [right]).

Table 2. Cell Frequency and Signaling Activities and Intracellular Expression of Signaling Markers per Single Cell to be Quantified

Cell Frequency and Signaling Activities	Intracellular Expression of Signaling Markers per Single Cell
1. Neutrophils	1. Phosphorylated-(p) signal transducer and activator of transcription 1 (STAT1)
2. Cluster of differentiation 27 (CD27)+ memory B (Bmem) cells	2. p(STAT3)
3. CD27- naïve B (Bnaive) cells	3. pSTAT5
4. CD56hiCD16-Natural Killer (NK) cells	4. pSTAT6
5. CD56loCD16+ NK cells	5. p nuclear factor kappa-light-chain-enhancer of activated B cells (NF- κ B)
6. CD4+CD45RA- T cells (CD4+ Tmem)	6. p mitogen-activated protein kinase 2 (MAPK2)
7. CD4+CD45RA+ T cells (CD4+ Tnaive)	7. pP38
8. CD4+Tbet+CD45RA-T cells (Th1)	8. prpS6
9. CD4+Tbet+CD45RA+ T cells	9. p extracellular regulated kinase (ERK)1/2
10. CD25+FoxP3+CD4+ T cells (Tregs)	10. p cyclic AMP response element-binding protein (CREB)
11. CD8+CD45RA- T cells (CD8+ Tmem)	11. total I κ B α
12. CD8+CD45RA+ T cells (CD8+ Tnaive)	
13. CD8+Tbet+CD45RA- T cells	
14. CD8+Tbet+CD45RA+ T cells	
15. TCR γ δ T cells	
16. CD14+CD16- classical monocytes (cMCs)	
17. CD14-CD16+ non-classical monocytes (ncMCs)	
18. CD14+CD16+ intermediate monocytes (intMCs)	
19. Monocytic myeloid-derived suppressor cells (M-MDSCs)	
20. Myeloid dendritic cells (mDCs), and	
21. Plasmacytoid dendritic cells (pDCs)	

Measurement of CyTOF will be performed by Dr. [REDACTED] and Dr. [REDACTED] ([REDACTED]). Two (2) CyTOF datasets will be generated and analyzed separately:

- *CyTOF Dataset 1* (Effect on endogenous immune responses to surgery): Changes in cell frequency and endogenous intracellular signaling activities from Visit 3 to Visits 4b and 5.
- *CyTOF Dataset 2* (effect on immune response to *ex vivo* stimulation): Changes in cell frequency and evoked intracellular signaling responses to *ex vivo* stimulations from Visit 3 to Visit 4a.

Cell frequencies will be expressed as percentages of gated singlets in the case of granulocytes, and as percentages of mononuclear cells in the case of all other cell types. For each cell type,

frequency features will be calculated as the difference in cell frequency between Visit 3 and Visit 4b or Visit 5 (Dataset 1) or Visit 3 and Visit 4a (Dataset 2).

For each cell type, basal signaling activities will be expressed as the median signal intensity (arcsinh transformed value) of each signaling protein.

Endogenous signaling changes in response to surgery will be expressed as the difference in median signal intensity (hyperbolic arcsine [arcsinh] ratio) between post-operative time points (Visit 4b, Visit 5) and the day of surgery, preoperative time point (Visit 4a).

Evoked signaling responses to stimulations will be expressed as the difference in median signal intensity (arcsinh ratio) between the stimulated and unstimulated condition. Changes in evoked signaling responses will be expressed as differences in evoked signaling responses between the Visit 3 (baseline) time point and the Visit 4a time point.

The high-dimensional data results will be further analyzed and presented using the iEN algorithm which is a penalized regression method particularly adapted to the analysis of highly-correlated data, as it eliminates redundant parameters while retaining interrelated parameters (for further details see [Section 8.1 General Considerations](#)). Data presentations will include multi-part visualizations (figures) (see [Appendix 1](#)).

8.4.2 Select Secondary Endpoints (High-Dimensional Data)

8.4.2.1 Change in Functional Status using the ActiGraph Wearable Device

The ActiGraph wearable device is used to monitor subjects' physical activity, mobility and sleep ([ActiGraph 2021](#)). Functional status including heart rate and sleep time will be collected during the whole study period except perioperative times. Changes in functional statuses comparing to the baseline will be calculated. The complete list of 62 ActiGraph measurements can be found in the ActiLife 6 User's Manual ([ActiGraph 2012](#)).

The ActiGraph high-dimensional data will be analyzed and presented using the EN algorithm which is a penalized regression method particularly adapted to the analysis of highly-correlated data, as it eliminates redundant parameters while retaining interrelated parameters (for further details see [Section 8.1 General Considerations](#)). Data presentations will include multi-part visualizations (figures) (see [Appendix 1](#)).

8.4.2.2 Effects of GRF6021 on Proteomics

Serial blood samples collected at baseline and all 3 perioperative time points (Visits 3, 4a, 4b, and 5) will be analyzed by the Somalogic SomaScan platform (Somalogic, Boulder, CO, USA), which provides a broad overview of proteomics changes by measuring approximately 7,000 proteins. It uses a highly multiplexed and high throughput aptamer based proteomic technology and deoxyribonucleic acid (DNA)-microarray-based detection. It provides concentration domain values as relative fluorescence units (RFUs). Details of sample collection and processing were included in the Laboratory Manual.

The proteomic high-dimensional data will be analyzed and presented using the EN algorithm which is a penalized regression method particularly adapted to the analysis of highly-correlated data, as it eliminates redundant parameters while retaining interrelated parameters (for further

details see [Section 8.1 General Considerations](#)). Data presentations will include multi-part visualizations (figures) (see [Appendix 1](#)).

CyTOF data and proteomics data may be combined for improving EN model performance. Additional exploratory analyses of CyTOF and proteomics data will be described in subsequent analysis plans.

10 SUMMARY OF CHANGES

Not applicable as this is the initial version.

11 APPENDICES

11.1 Appendix 1: Figure Descriptions/Shells

Figure 14.1.1: Subject Disposition (CONSORT Diagram)

[figure not shown]
[figure not shown]

Figure 14.2.1: Boxplot Comparing the Elastic Net Values from a Cross-validated Model of CyTOF Features Between the Active GRF6021 Group and Placebo Group

Note: The above figure is for illustration purposes only. The figure does not represent the data of the study. Colors and symbols may change. Axis titles or values may also change.

In figure 14.2.1, y-axis is the calculated Elastic Net Values from cross-validated model of CyTOF features.

[figure not shown]
Similar figures:

Figure 14.2.2: Boxplot Comparing the Elastic Net Values from a Cross-validated Model of ActiGraph Features between the Active GRF6021 Group and the Placebo Group

Figure 14.2.3: Boxplot Comparing the Elastic Net Values from a Cross-validated Model of Proteomics Features (SomaScan platform) Between the Active GRF6021 Group and the Placebo Group

Figure 14.2.4: Boxplot Comparing the Elastic Net Values from a Cross-validated Model of Combined CyTOF Features and Proteomics Features (SomaScan platform) Between the Active GRF6021 Group and the Placebo Group

Figure 14.2.5: Correlation Network of CyTOF Features Represented by a Minimum Spanning Tree

Note: The above figure is for illustration purposes only. The figure does not represent the data of the study. Colors and symbols may change. Axis titles or values may also change.

In Figure 14.2.5, each dot represented significantly associated features (after Bonferroni adjustment), different color indicated different feature types, such as cell frequency features and cell signaling features. Lines pointed the increased immune features in the GRF6021 group or in the placebo group.

[figure not shown]
Similar figures:

Figure 14.2.6: Correlation Network of ActiGraph Features Represented by a Minimum Spanning Tree

Figure 14.2.7: Correlation Network of Proteomics Features Represented by a Minimum Spanning Tree

Figure 14.2.8: Correlation Network of CyTOF and Proteomics Features Represented by a Minimum Spanning Tree from Combined CyTOF and Proteomics Data

Figure 14.2.9: Identified CyTOF Features Showing on the Correlation Network Based on Elastic Net Regression Models

Note: The above figure is for illustration purposes only. The figure does not represent the data of the study. Colors and symbols may change. Axis titles or values may also change.

In Figure 14.2.9, identified CyTOF immune features from Elastic Net were listed and mapped on the correlation network, up-arrow indicated up-regulation in the GRF6021 group and down-arrow indicated down-regulation in the GRF6021 group.

Similar figures:

Figure 14.2.10: Identified ActiGraph Features Showing on the Correlation Network Based on Elastic Net Regression Models

Figure 14.2.11: Identified Proteomics Features Showing on the Correlation Network Based on Elastic Net Regression Models

Figure 14.2.12: Identified CyTOF and Proteomics Features Showing on the Correlation Network Based on Elastic Net Regression Models from Combined CyTOF and Proteomics Data

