10.4.2 ANALYSIS OF THE PRIMARY ENDPOINT

The study is not powered to detect significant changes in the immune signatures; however, using available data from analysis of this endpoint, including changes from baseline, the primary interest is to detect

immune features (and proteomic features) that separate the two groups. Machine learning approaches using cross-validation algorithms will be the primary approach for such analysis. The output of this analysis will produce a list of significant immune and/or proteomic features.

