10.5 SAMPLE SIZE

A total of approximately 45 subjects will be enrolled with the aim of having 40 evaluable subjects randomized in a 1:1 ratio to active treatment or placebo. The primary endpoint of this study (differences in immunological and/or proteomic signatures among patient groups), the principal computational approach (machine learning) used, and the exploratory nature of the study prevent a traditional power analysis. However, a sample size of 2 x 20 subjects was sufficient to detect relevant differences in previous studies examining interventions expected to have a similar effect size ([Aghaeepour 2017](#)).

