7.4 Randomization and Blinding

The study will be randomized in a 1:1 ratio (active: placebo), stratified by sex and surgical joint (hip, knee) to assure a balanced distribution of evaluable male and female subjects in both treatment groups.

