8 STATISTICAL METHODOLOGY

8.1 General Considerations

This section of the SSAP presents the analytical approaches that are anticipated for the high-dimensional data from AKST6021-211. Analysis of data from the clinical secondary endpoints from AKST6021-211 are detailed in the SAP (08OCT2020). These analytical approaches to the high-dimensional data may at times require modifications due to unanticipated features.

Deviations from analyses summarized in this document will be noted in the Clinical Study Report (CSR).

All analysis dataset preparations and statistical analyses will be performed using R version 4.0.2 or higher.

The high-dimensional data results from AKST6021-211 will be analyzed using the immunological elastic net (iEN) algorithm for the primary endpoint and standard elastic net (EN) modeling for the ActiGraph and proteomics data. Models utilizing iEN or EN utilize a penalized regression method particularly adapted to the analysis of highly-correlated data, as it eliminates redundant parameters while retaining interrelated parameters (Zhou 2005, Culos 2020). All parameters will be set to default except for $\alpha = 0.5$ (to limit the number of selected features, but account for the most important components of each intracorrelated module) and standardized as equal to FALSE to enable the specific modifications described in [Section 8.4 Efficacy Analyses](#). A two-layer leave-one-out cross-validation strategy will be employed where the final model will have optimized the segregation of active versus placebo treatment groups. The internal layer will optimize the free parameters of the model, and the external layer will evaluate model performance. Data presentations will include a flow diagram of the progress of the 2 groups (GRF6021 and placebo) through enrollment, intervention allocation, follow-up, and data analysis. Additional multi-part visualizations (figures) for the primary endpoint (CyTOF) and select secondary endpoints (ActiGraph, proteomics) will be developed (see [Appendix 1](#)).

Unless otherwise specified, an alpha of 0.05 will be used for significance testing. For multiple comparisons due to the high dimensionality, the false discovery rate using the Benjamini-Hochberg method will be controlled and the corrected p-values will be reported as q-values.

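### The elastic-net feature lists are called significant in the protocol, but no error-control rule in the SAP is tied to them, and a list is likely even with no drug effect

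*SAP*

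**What the plan says.** Protocol 10.4.2 makes cross-validated machine learning the primary approach and states: "The output of this analysis will produce a list of significant immune and/or proteomic features". Protocol 10.4.8 says that multiplicity will not be adjusted for.

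SAP 8.1 specifies the iEN for CyTOF and a standard elastic net for ActiGraph and proteomics, with nested leave-one-out cross-validation. "The internal layer will optimize the free parameters of the model"; the external layer judges performance. On settings it says "All parameters will be set to default except for" a mixing value of 0.5 and switched-off standardization. It does not say whether the penalty is the one that minimises cross-validated error or the one from the one-standard-error rule.

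SAP 8.1 also sets alpha at 0.05 and controls the false discovery rate by Benjamini-Hochberg, reported as q-values. In SAP Appendix 1, the note to Figure 14.2.5 says that the dots of the CyTOF correlation network are features significant after Bonferroni adjustment. The note to Figure 14.2.9 says that "identified CyTOF immune features from Elastic Net were listed and mapped on the correlation network, up-arrow indicated up-regulation in the GRF6021 group". Figures 14.2.10 to 14.2.12 do the same for ActiGraph, proteomics and the combined data.

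**The concern.** A penalty tuned by cross-validation is chosen for prediction. It puts no bound on the chance that a feature without any treatment effect keeps a nonzero coefficient. Elastic-net coefficients also come without p-values, so a q-value or Bonferroni rule does not reach them unless the plan says how.

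These lists are the most concrete product of the primary endpoint: named cell types and signaling markers, each with a direction attributed to GRF6021. If the plan is followed as written, chance selections can be presented as drug effects under the protocol's word 'significant', and two analysts could reasonably produce different lists.

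**Working it through.** The documents give no false-selection rate, so there is no figure to reproduce. The question is how often a list would appear if GRF6021 did nothing.

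**Inputs from the documents**
- Subjects: SAP 7.3 says that "enrollment ended with 37 evaluable subjects". Allocation is 1:1 (SAP 7.4). The split by arm is not given; 18 versus 19 is assumed, with one run at 20 versus 20.
- Features: SAP Table 2 has 21 cell types and 11 markers. One change period gives 21 + 21×11 = 252. Dataset 1 with two postoperative visits gives 21×2 + 21×11×2 = 504.
- Mixing value 0.5, no standardization, leave-one-out tuning (SAP 8.1).

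**Assumptions**
- Dataset 2 has 21 + 21×11×3 = 714 features if there are three stimulations; the SAP does not give their number.
- Features are independent, or in blocks of 21 or 42 with correlation 0.3 to 0.8.
- 'Identified' means a nonzero coefficient in the fit to all subjects.
- The iEN prior weights are not given and are not modelled. The model family is not named, so least squares and logistic were both run.

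**Fit.** For each penalty λ, minimise loss + λ(0.5·Σ|b| + 0.25·Σb²), choose λ by leave-one-out error, and count nonzero b. Allocation is unrelated to the features in every data set.

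| Null scenario (trials) | Any feature listed, error-minimising λ | Any feature listed, one-SE λ | Median listed when any (error-minimising) |
|---|---|---|---|
| Least squares, 504, independent (150) | 0.69 | 0.50 | 15 |
| 504, blocks of 21, corr. 0.3 (150) | 0.70 | 0.45 | 13 |
| 504, blocks of 21, corr. 0.6 (150) | 0.60 | 0.39 | 12 |
| 504, blocks of 42, corr. 0.8 (150) | 0.57 | 0.32 | 7 |
| 504, blocks of 21, corr. 0.5, unequal scales (150) | 0.61 | 0.29 | 7 |
| 252, blocks of 21, corr. 0.5 (150) | 0.69 | 0.44 | 12 |
| 714, blocks of 21, corr. 0.5 (150) | 0.68 | 0.53 | 15 |
| 504, blocks of 21, corr. 0.5, 20 vs 20 (150) | 0.65 | 0.39 | 10 |
| R glmnet, least squares, 504, corr. 0 / 0.5 (100 each) | 0.65 / 0.65 | 0.40 / 0.46 | 13 / 14 |
| R glmnet, logistic, 504, corr. 0 / 0.5 (60 each) | 0.65 / 0.53 | 0.43 / 0.33 | 17 / 14 |
| Nested leave-one-out, 252, corr. 0.5 (87) | 0.75 | not run | not recorded |

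The range is 0.53 to 0.75 with the error-minimising penalty and 0.29 to 0.53 with the one-standard-error rule. Monte Carlo standard errors are about √(0.65×0.35/150) = 0.04 for 150 trials and √(0.6×0.4/60) = 0.06 for 60.

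**Two CyTOF models.** If they were independent, the chance that at least one lists a feature is 1 − (1 − p)². For p = 0.57 and 0.70 this is 0.82 and 0.91; for p = 0.30 and 0.50 it is 0.51 and 0.75. They share subjects, so this is only a guide.

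**If the SAP's own rules were applied.** Per-feature t-tests on all 504 features, 1,500 null trials per setting:
- Benjamini-Hochberg (some ordered p(k) ≤ 0.05k/504): any feature passes in 0.054 (corr. 0) and 0.043 (corr. 0.5).
- Bonferroni (smallest p ≤ 0.05/504): 0.054 and 0.041.

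A feature that must be both selected and pass can appear no more often than this.

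**If listing required the outer layer to separate the arms.** In the nested run, features were listed and the held-out scores separated the arms at nominal one-sided rank-sum p < 0.05 in 12 of 87 trials = 0.138. Leave-one-out scores are dependent between subjects, so the nominal rank-sum level cannot be relied on.

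**The case against.** **The lists may already be filtered.** Benjamini-Hochberg control sits in the SAP's general section, and Figure 14.2.9 maps its features onto the correlation network. The only CyTOF network described is that of Figure 14.2.5, whose dots passed Bonferroni. If the list is confined to those dots, false listing is already about 4 to 5%. So a reader who infers that the plan has no error control at all goes too far: it has two rules. What remains is that the note says the elastic-net features are listed and mapped, not that those failing Bonferroni are dropped. It is also unclear which of the two rules would govern.

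**The outer layer is a safeguard.** Figure 14.2.1 shows cross-validated scores by arm, so a careful reader of a null trial would often see poor separation beside the list. In the nested run only about 14% of null trials had both a list and nominal separation. This stands as mitigation, but the SAP does not make listing depend on it.

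**The study is exploratory.** Protocol 10.5 says that its features "prevent a traditional power analysis", protocol 10.4.2 itself says the study is not powered, and the SAP calls the features identified rather than significant. This lowers the severity. It does not support the protocol's word, or directional arrows without a measure of uncertainty.

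**The figure images are not available.** Whether a shell already carries a selection frequency cannot be checked; only captions and notes can be read.

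**Conclusion.** The concern holds in this form: neither multiplicity rule is tied to the elastic-net lists, listing does not depend on outer-layer performance, and the protocol calls the output significant. Under no drug effect, roughly 3 to 7.5 of 10 trials per CyTOF model would list at least one feature: about 5.5 to 7.5 with the error-minimising penalty, which is the natural reading of an inner layer that optimises, and 3 to 5 with the one-standard-error rule. Even the lowest value, 0.29, is nearly six times the SAP's 0.05.

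It is tempting to infer one fixed rate, or that most null trials would certainly produce a list. The documents do not support that. The rate depends on a penalty rule they do not name, on the feature count, scale and correlation, on the model family, and on iEN weights that could move it either way. It also assumes that the list is not confined to the Bonferroni-filtered network. The point concerns how the primary result is labelled and read, not the trial's value as exploration. It should be settled before the lists are produced.

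**What to change.** 1. In SAP 8.1 and the notes to Figures 14.2.9 to 14.2.12, print each listed feature's univariate q-value, computed over all features offered to that model and not only the selected ones.
2. Reserve 'significant' for features with q ≤ 0.05. Label the others 'selected, not tested', meaning that selection by the elastic net is not itself a test. Reword protocol 10.4.2 to match, and say whether the network in Figure 14.2.9 is limited to the Bonferroni-significant dots of Figure 14.2.5.
3. Name the penalty rule.
4. Beside each list, report a p-value for the outer-layer performance, obtained by permuting treatment within the randomization strata (sex and joint) and repeating the whole nested procedure. A nominal rank-sum gate is not enough, as the 14% shows.
5. If selection frequencies are shown, obtain them by subsampling subjects without replacement, or keep duplicates of a subject in the same fold. An ordinary bootstrap with leave-one-out tuning leaves copies of the held-out subject in the training data. In a small null check (36 data sets, 504 features, correlation 0.5, least squares), non-empty lists rose from 75% with ordinary tuning to 100% with bootstrap refits (median 5.5 versus 31 features); keeping duplicates together gave 58%.

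Cost: wording in the SAP, figure notes and protocol, and more computing, chiefly for the permutations. No new data are needed. The lists of 'significant' features will be shorter and may be empty.
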